7.3 Justification of the Trial Design

7.3.1 Justification for Design and Parameters

This trial is designed to document the efficacy of Lumentin® 44 to show contrast difference between the small bowel lumen and the small bowel wall (mucosal lining) as compared to the comparators and to investigate safety. A parallel groups design has been

chosen as a cross-over design is considered both unethical, for reason of irradiation, and logically impossible.

Data from an explorative trial [1] clearly indicates that the foam provided bowel loops with a black lumen and a large difference in contrast density between the lumen and surrounding small bowel wall (mucosal lining). The diagnostic readability of CT-examinations was highly accepted by the radiologists. The foam was also able to fill the small bowel from pylorus to cecum on par with routinely used contrast agents and was well accepted by the subject with no serious adverse events. The observed adverse events were all mild with no need to intervene.

The primary efficacy variable has been defined to be able to observe the contrast difference between the small bowel lumen and the small bowel wall (mucosal lining) in the whole length of the small bowel. The ability of the contrast agent to fill the small bowel is therefore reflected in the primary efficacy variable.

Secondary objectives have been chosen to investigate the safety profile, the filling property of the contrast agent, the stability of Lumentin® 44 after administration, the diagnostic potential and how the patients experience the contrast agents properties with respect to taste, smell etc.

The trial is not designed to investigate Lumentin® 44 with respect to diseases of the small bowel. No patients eligible for this trial have a clinical suspicion of a bowel disorder, viz. the bowel contrast agents are only used for demarcating the small bowel on the CT-scans. The use of Lumentin® 44 in this trial will thus not influence any diagnostic performance of bowel diseases. Future trial with Lumentin® 44 will be designed to investigate the diagnostic potential for small bowel disorder with Abd-CT.

7.3.2 *Justification for Drug, Route, Dosage and Treatment Duration*

Comparators used in the trial are both standard care treatment used for patients referred to abdominal CT-scan examinations.

Subjects in a previous explorative trial [1] were given 0.9 -1.5 L foam to take orally and 23 out of the 25 subjects could consume more than 0.9 L of the foam. The small bowel filling properties of the foam was on par with the normally used contrast agents, diluted Omnipaque® and Movprep®. A dose of 1 000 ml \pm 200 ml was therefore selected. Both route and treatment duration are according to standard praxis.

8 TRIAL POPULATION

The trial population will consist of subjects who are referred to CT-examination of the abdomen. The subjects must be able to provide written informed consent and meet all the inclusion criteria and none of the exclusion criteria.

8.1 Inclusion Criteria

Subjects will be entered into this trial only if they meet all of the following criteria:

1. Subjects of either gender at least 18 years at the time of signing the informed consent.
2. Females must either present a negative pregnancy test or be surgically sterile (hysterectomy or tubal ligation) or postmenopausal (i.e. experienced 12 consecutive months without menstruation)

3. Having a clinical indication for CT-examination of the abdomen
4. Having fasted (drinking allowed) for at least four hours prior to the intake of the contrast agent
5. Patients participating in concurrent oncology trial must either participate in the follow up phase of the clinical trial and currently receive no trial drug treatment since at least 6 weeks, or receive a reduced maintenance dose of the trial treatment
6. Following verbal and written information about the trial, the subject must provide signed and dated informed consent before any trial related activity is carried out.

8.2 Exclusion Criteria

Subjects will not be enrolled if they meet any of the following criteria:

1. IV administration of iodine is contraindicated
2. Clinical suspicion, according to medical record, of fistula formation and/or leakage
3. Having swallowing disorders preventing intake of the contrast agents
4. Referral indication of small bowel disease(s)
5. Known allergy to egg albumen
6. Known sensitivity to any of the components of the investigational product or comparators
7. Having known manifest thyrotoxicosis
8. Having known phenylketonuria
9. Having known Glucose-6-phosphatase deficiency
10. Has taken any medication, absorbed through the small bowel, less than four hours before intake of the investigational product or comparators
11. Being, in the opinion of the investigator, unlikely to comply with the clinical trial protocol
12. Previously randomised to participate in this trial
13. Participating in, or having participated in another, non-oncology clinical trial where the final trial treatment was given within the last 6 weeks
14. Participating in an oncology clinical trial where the final full (i.e. non-maintenance) trial treatment was given within the last 6 weeks

8.3 Subject Withdrawal and Replacement

Subjects may withdraw from the trial at any time and for any reason without prejudice to his or her future medical care.

Subjects must be withdrawn under the following circumstances:

- The subject withdraws consent,
- The subject is unable to drink at least 750 mL of Lumentin® 44 or at least the lowest recommended dose, according to the general praxis of care at the department of “Verksamhetsområde Bild och funktion Skånes Universitetssjukhus”, of Omnipaque® and Movprep®
- Violation of eligibility criteria

Subjects may be required to withdraw after discussion with the Sponsor and/or Investigator for the following reasons:

- AEs,
- Use of prohibited medication (see Section 9.7),
- At the discretion of the Investigator,
- Violation of eligibility criteria,

In all cases, the reason(s) for withdrawal must be recorded on the eCRF. If a subject is prematurely withdrawn from the trial for any reason, the Investigator must make every effort to perform the evaluations described for the Early Termination Visit (see Section 12).

If a subject has withdrawn informed consent and still agrees to attend the Early Termination Visit, this will be documented on the eCRF.

For subjects who are withdrawn after they receive the trial drug, the Early Termination page will be completed in the eCRF.

Subjects who are withdrawn from the trial will be provided care according to the judgement of the investigator. Normal praxis at the clinic is to perform the CT-scan even if the subject cannot consume the recommended volume of the contrast agent.

Subjects who withdraw after randomisation will not be replaced.

8.4 Planned Sample Size and Number of Trial Centres

It is planned to randomise 40 evaluable subjects to the Lumentin arm and 20 subjects to each of the Omnipaque and Movprep arms. To cover for a 10% drop out rate a total of 93 subjects will be randomised.

Randomisation will be terminated when 40:20:20 evaluable subjects are reached in respective arm. See Section 13.6 for a discussion of sample size.

8.5 Subject Identification and Randomisation

Subjects referred to CT examination of the abdomen will receive an invitation to the CT examination by letter. An advertisement letter informing about the trial will be included in this referral letter.

All referrals for abdominal CT are read and prioritized by the investigator/sub-investigator. Those subjects, irrespective from which medical clinic, who the radiologist think are possible candidates for the trial, will have the advertisement letter added to the referral letter sent home to them with date and time for their CT-examination.

An invitation log will be kept with names of those receiving the advertisement letter. Subjects will subsequently be contacted by and asked if they are interested in participation. Those interested will be sent the subject information leaflet.

All subjects receiving the patient information leaflet will receive a screening number consisting of S followed by three digits: S-XXX starting with S-101.

The Investigator will allocate the screening numbers in ascending order.

Enrolled subjects who drop out of the trial before randomisation will retain their screening number.

Randomisation will occur at the clinic on the day of examination when all screening procedures have been performed and eligibility for the trial confirmed. Each randomised subject will receive a unique randomisation number consisting of R followed by three digits: R-XXX starting with R-101. Randomisation numbers will be allocated in strict ascending order according to a randomisation list

Randomised subjects who terminate their trial participation for any reason, regardless of whether trial drug was taken or not, will retain their randomisation number.

Subjects will be randomised on a 1:1:1 basis to Lumentin® 44, diluted Omnipaque® or Movprep®. The randomisation will be in blocks and stratified by gender as the drinking capacity differs between males and females.

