	
A post- examination clinical chemistry blood sample is taken prior to the subject is leaving the clinic and occurrence of any adverse events is recorded.
 
The subjects are free to leave the clinic after 30 minutes post CT-examination.
 
For safety reasons, subjects will be contacted, within 12 to 48 hours after the examination, by the investigator and asked about occurrence of any adverse event. No other follow-up is planned.

Trial population	The trial population will consist of subjects who are referred to CT-examination of the abdomen. The subjects must be able to provide written informed consent and meet all the inclusion criteria and none of the exclusion criteria.
Number of subjects	
The target is to randomise 88 subjects with the goal to reach 80 evaluable subjects.
 
However, due to the duration of the trial is only one day for the subject, randomisation will stop when 80 evaluable subjects have completed the trial.
 
Randomisation will be skewed so that 40 subjects will be allocated to the Lumentin arm and 20 each to the Omnipaque and Movprep arms.

Main inclusion criteria	
Subjects will be entered into this trial only if they meet all of the following criteria:
 
1. Subjects of either gender at least 18 years at the time of signing the informed consent.2. Females must either present a negative pregnancy test or be surgically sterile (hysterectomy or tubal ligation) or postmenopausal (i.e. experienced 12 consecutive months without menstruation)3. Having a clinical indication for CT-examination of the abdomen4. Having fasted (drinking allowed) for at least four hours prior to the intake of the contrast agent5. Patients participating in concurrent oncology trial must either participate in the follow up phase of the clinical trial and currently receive no trial drug treatment since at least 6 weeks, or receive a reduced maintenance dose of the trial treatment6. Following verbal and written information about the trial, the subject must provide signed and dated informed consent before any trial related activity is carried out.

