Statistical analyses	
The sample size estimation is based on a similar variable as the primary variable in this trial, i.e. the difference in contrast density in HU between bowel lumen and wall (mucosal lining), expressed as the mean of 9 measurement performed in the 5 selected sub-segments of the small bowel. At each measurement site, the equipment gives a mean value (given by the software of the X-ray equipment in Hounsfield Units) and a standard deviation (for the pixels in the Region of Interest, ROI). This mean value is from now on called “mean contrast density”.
 
In order to reach a 78 % probability (power) to detect (i.e. get a two-sided p-value less than 5 %) assuming a difference of 1.50 between the groups for the mean difference in contrast density and a standard deviation of 2.00 (assumptions based on an earlier trial, [1]) a total of 40 fully evaluable is needed in the Lumentin group and 20 in each of the comparator groups, i.e. a total of 80 fully evaluable subjects
 
The randomisation will be stratified by gender as the drinking capacity on average differs between males and females.
 
Descriptive statistics will be used to describe the results. When testing the hypotheses of equality between the groups p-values (two-sided) will be calculated by means of the Wilcoxon rank sum test or Fisher's exact test depending on the distribution of the variable of interest.

-----------------------------	---

1.1 Schedule of Events:

Visit/Contact	0 Screening ^{a)}	1 CT-scan	2 Telephone interview and early termination ^{b)}
Day	-28 to -1	0	1-2
Visit window			12-48 hours
Subject information	X	X	
In/exclusion criteria		X	
Informed consent		X	
Pregnancy test ^{c)}		X	
Randomisation		X	
Subject demographics (incl. height and weight)		X	
Concomitant treatment		X	X
Concomitant illnesses		X	
Medical history		X	
Blood sample (clinical chemistry) ^{d)}		X	
Adverse event(s)		X	X
Dispensing of contrast agent		X	
Administration of Iodine contrast		X	
CT Scan		X	
Evaluation of contrast difference		X	
Evaluation of extension and distension composite score		X	
Evaluation of diagnostic ability		X	
Evaluation of contrast agent degradation		X	
Subject assessment of taste, smell, consistency etc.		X	
Compliance		X	

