13.6 Determination of Sample Size

13.6.1 Sample size (per group)

The standard deviation of the primary variable (i.e. the difference in contrast density in HU between bowel lumen and wall (mucosal lining), expressed as the mean of 9 measurements performed in the 5 selected sub-segments of the small bowel) is estimated from the first pilot clinical study of abdominal CT examinations on healthy volunteers using a slightly different formulation (L60). Based on data from that study [1] it is assumed that the standard deviation will be around 2.00 and the difference between Lumentin® 44 and Omnipaque® as well as the difference between Lumentin® 44 Movprep will be 1.50. Then 40 fully evaluable patients in the Lumentin group and 20 patients in each of the comparator groups are needed to get 78 % power for each of the two primary objectives (no adjustment for multiplicity). This means that the total probability in the trial to get a p-value less than 5 % in the test of both the primary objectives is $0.78 \times 0.78 = 0.61$.

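### Section 8.5 randomises 1:1:1, but the synopsis, 8.4 and 13.6.1 need 40:20:20; the total randomised (88 or 93) and the stopping rule also conflict

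*Combined protocol and SAP*

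**What the plan says.** **Ratio.** Section 8.5: "Subjects will be randomised on a 1:1:1 basis to Lumentin® 44, diluted Omnipaque® or Movprep". It adds that allocation is blocked and stratified by gender, and "Randomisation numbers will be allocated in strict ascending order according to a randomisation list". Four other places give a different split:

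- Synopsis, Number of subjects: "Randomisation will be skewed so that 40 subjects will be allocated to the Lumentin arm and 20 each to the Omnipaque and Movprep arms".
- Synopsis, Statistical analyses: "a total of 40 fully evaluable is needed in the Lumentin group and 20 in each of the comparator groups".
- Section 8.4 plans 40 evaluable on Lumentin and 20 on each comparator.
- Section 13.6.1: "40 fully evaluable patients in the Lumentin group and 20 patients in each of the comparator groups are needed".

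**Total.** The synopsis targets 88 randomised. Section 16.5.1 closes enrolment at 88 randomised if the required number of evaluable subjects has not been reached sooner. Section 8.4: "To cover for a 10% drop out rate a total of 93 subjects will be randomised".

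**Stopping.** Synopsis: "randomisation will stop when 80 evaluable subjects have completed the trial". Section 8.4: "Randomisation will be terminated when 40:20:20 evaluable subjects are reached in respective arm". Section 16.5.1 refers only to the total number of evaluable subjects requested, subject to the cap of 88.

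**The concern.** Section 8.5 is the operative instruction for whoever generates the randomisation list, and it is the one place that disagrees with the sample-size section. Nothing in the protocol says which section prevails. Once the list is in use, the allocation cannot be repaired in the analysis.

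A list built as 8.5 says would under-supply the Lumentin arm by about a third. Safety, bowel filling and foam degradation are named secondary objectives, and section 9.6 intends to use the data to advise on how much of the product to use.

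The 8.4 stopping condition would then not be met within either stated total. The only way to force 40:20:20 from a 1:1:1 list would be to close the comparator arms when full and give Lumentin to everyone after that. Later Lumentin subjects would then have no concurrently randomised controls.

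Separately, the person closing enrolment has two totals and two evaluable-count rules to choose from.

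**Working it through.** **Inputs.** Difference 1.50, SD 2.00, 40 v 20 evaluable, power 78% per comparison (13.6.1); two-sided 5% (13.4.1); drop-out 10% and total 93 (8.4); total 88 (synopsis, 16.5.1); ratio 1:1:1 (8.5).

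**1. The plan's own figure.** Normal approximation: z = 1.5 / (2 × √(1/40 + 1/20)) = 1.5 / (2 × √0.0750) = 2.739. Power = Φ(2.739 − 1.960) = 0.782. The stated 78% reproduces, and it belongs to 40:20, that is, to 2:1:1.

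**2. What each ratio delivers.** Expected numbers, with evaluable = randomised × 0.9:

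| Ratio | Total randomised | Lumentin randomised | Lumentin evaluable |
|---|---|---|---|
| 1:1:1 | 88 | 88/3 = 29.3 | 26.4 |
| 1:1:1 | 93 | 93/3 = 31 | 27.9 |
| 2:1:1 | 88 | 44 | 39.6 |
| 2:1:1 | 93 | 46.5 | 41.9 |

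Forty evaluable on Lumentin at 1:1:1 needs 3 × 40/0.9 = 133.3, so 134 randomised (135 with equal arms). 134 − 88 = 46 above the cap.

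**3. Could chance imbalance rescue a 1:1:1 list?** The block size is not stated. Assume fixed blocks in two gender strata, and take the most favourable gender split and the most favourable order within each unfinished block. The largest possible number randomised to Lumentin is:

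| Block size | 3 | 6 | 9 | 12 |
|---|---|---|---|---|
| At 88 randomised | 30 | 32 | 33 | 32 |
| At 93 randomised | 32 | 33 | 33 | 36 |

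Forty is out of reach for these block sizes even with no drop-out.

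**4. The synopsis stopping rule under 1:1:1.** 80/3 = 26.7 evaluable per arm, not 40:20:20.

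**5. Power under each ratio.** The variance factor at 26.67 per arm is 2/26.67 = 0.0750, the same as 1/40 + 1/20, so per-comparison power is again 0.782. With 88 randomised and 10% drop-out, 26.4:26.4 and 39.6:19.8 both give a factor of 0.0758 and power 0.778. The primary tests lose nothing to 1:1:1.

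**6. What is lost on Lumentin.** For an adverse event never observed, the one-sided 95% upper bound is 1 − 0.05^(1/n): 6.6% at n = 44 and 9.8% at n = 29. Confidence intervals for Lumentin-only summaries widen by √(39.6/26.4) = 1.22, about 22%.

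**7. The two totals.** 80 × 1.10 = 88, whereas 80/0.9 = 88.9, so 89; rounding up by arm gives 45 + 23 + 23 = 91. Neither calculation gives 93. With independent 10% drop-out and 2:1:1 allocation:

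| Randomised | P(at least 80 evaluable in total) | P(at least 40, 20 and 20 by arm) |
|---|---|---|
| 88 (44:22:22) | 0.48 | 0.21 |
| 93 (47:23:23) | 0.92 | 0.59 |

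The choice of total and the choice of stopping rule therefore affect each other.

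**The case against.** Four points can fairly be made for the plan.

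- **The intention is not in much doubt.** Four statements, including the sample-size section, say 40:20:20 and one says 1:1:1, which looks like an uncorrected sentence. That helps decide how to fix it, but it does not protect a list built from the section headed randomisation.
- **The primary analysis is not damaged.** Success requires both tests to be significant, and on that criterion equal allocation is slightly better. Simulated joint Wilcoxon power is about 0.59 at 40:20:20 and 0.62 at 27 per arm. This stands. The protocol also sets no precision or event-detection target for Lumentin-only data, so the 6.6% v 9.8% bounds and the 22% are yardsticks applied here, not missed specifications.
- **The stopping rules are close.** Since 40 + 20 + 20 = 80, the two evaluable-count rules may be one target stated twice. Under 2:1:1 they nearly coincide and part only when drop-out is uneven across arms. This makes it the least serious of the three conflicts. The large gap (26.7 per arm) arises only in combination with 1:1:1.
- **Reaching 40 is not strictly impossible.** Blocks of 24 or 30 would allow 40 on Lumentin at either total, but only at an extreme gender split and with no Lumentin drop-out. Section 8.4 read alone has no cap, so 1:1:1 would meet its rule at about 134 randomised; 16.5.1 prevents that. The practical conclusion does not change.

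**Conclusion.** The plan is wrong as written. The 1:1:1 ratio in 8.5 is incompatible with the 40:20:20 used everywhere else, and 93 in 8.4 is incompatible with the cap of 88 in 16.5.1. The two evaluable-count rules agree only if evaluability happens to fall in the planned proportions.

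The ratio is the serious item and must be corrected before the list is used. Following 8.5 would cost about a third of the planned Lumentin arm: about 29 instead of 44 exposed, and 26 instead of 40 evaluable. It costs no per-comparison power.

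The counts assume the protocol's own 10% drop-out, equal across arms. The statement that 40 is out of reach even without drop-out also assumes fixed blocks of 12 or fewer. The totals and stopping rule are secondary, but they should be settled in the same edit.

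**What to change.** 1. **Section 8.5:** change the ratio to 2:1:1, with block sizes in multiples of 4 within each gender stratum. Check the randomisation list against this before use.
2. **Total:** give one number in the synopsis, 8.4 and 16.5.1, with the drop-out formula behind it. Keeping 88 (44:22:22) adds no patients to the current cap, but the protocol should then say that about 79 evaluable are expected (39.6 + 19.8 + 19.8 = 79.2, power about 0.78). It should also give the chances of reaching 80 in total (about 48%) and 40:20:20 by arm (about 21%). If the sponsor wants the targets met more often, a higher cap is needed; 93 gives about 92% and 59%.
3. **Stopping rule:** state one rule in the synopsis, 8.4 and 16.5.1, either 80 evaluable in total or 40:20:20 by arm, in both cases subject to the cap. If the by-arm rule is kept, say what happens when one arm fills before the others, which 8.4 leaves open.

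The cost is wording in four places and a check of the list. Extra patients arise only if the sponsor chooses a total above 88.

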9 INVESTIGATIONAL PRODUCTS

9.1 Investigational products

9.1.1 Lumentin® 44

Lumentin® 44 Dispersion will be manufactured and released by Bioglan AB, [name], Sweden.

Table 1: Lumentin® 44 Dispersion

Ingredients	Lumentin® 44 Dispersion
	Concentration (g/100g)
Egg White Powder	1.93
Sodium dihydrogen phosphate dihydrate (NaH ₂ PO ₄ • 2H ₂ O) ¹	0.19
Dibasic potassium phosphate (K ₂ HPO ₄) ¹	0.63
Xanthan gum ¹	0.48
Flavour ²	0.24
Water, purified ¹	96.53

1) *Ph. Eur.: European Pharmacopoeia*

2) *The flavour mixture contains vanillin, Propylene Glycol (E1520) and water and belongs to a product range registered under a DMF in the US.*

Lumentin® 44 Foam

The final preparation of the investigational product, Lumentin® 44, will be performed at the clinic, see appendix 1, Lumentin® 44 dispersion whipping protocol

Lumentin® 44 contains the exact same ingredients as Lumentin® 44 Dispersion, see table 1, except for added air due to the whipping process.

9.1.2 *Diluted Omnipaque®*

Omnipaque® 240 mg I/mL is manufactured by GE Healthcare AS, [name], Norge.

Table 2: Omnipaque® 240 mg I/mL

Ingredients	Concentration (mg/mL)
Iohexol	518
Iodine equivalent	240
Tromethamine	1.21
Edetate calcium disodium	0.1
Hydrochloric acid	1
Sodium hydroxide	1

¹ For pH adjustment only

Diluted Omnipaque®

30 ml of Omnipaque® 240 mg I/mL will be mixed with 970 ml water.

The final preparation of the investigational product, diluted Omnipaque®, will be performed at the clinic.

9.1.3 *Movprep®*

Movprep® is distributed by Norgine BV, [name], The Netherlands.

Movprep® is distributed as two dose units, Unit A and Unit B.

Table 3: Movprep®

Ingredients	Content (g)
Unit A	-
- Macrogol 3550	100
- Sodium Sulphate, waterfree	7.500
- Sodium Chloride	2.691
- Potassium Chloride	1.015
Unit B	-
- Ascorbic Acid	4.700
- Sodium Ascorbate	5.900

Preparation of Movprep®

Dose Units A and B are dissolved in 1000 ml water.
The final preparation of the investigational product, Movprep® will be performed at the clinic.

